2.3.5 Sample size

$$N = 2 * \left[\left(t_{\frac{\alpha}{2}} + t_{\beta} \right) * \frac{S}{\delta} \right]^2$$

Given that $\alpha = 0.05$ and $\beta = 0.1$, the critical values $t_{\frac{\alpha}{2}}$ and t_{β} are calculated as:

$$t_{\frac{\alpha}{2}} = 1.96, \quad t_{\beta} = 1.28$$

From the Ref. [18], $S = 16.1$, $\delta = 32.3$. After calculation, we obtained

$$N > 5.21$$

Therefore, the minimum sample size $N_{min} = 6$. In this study, we recruited 6 juveniles with SMA type II.

2.4 Statically Analysis

All statistical analyses were conducted on data collected from all subjects and performed with the MATLAB R2017b (MathWorks), and Microsoft Excel. Using a paired-sample t-test to analyze the significant difference of data. We consider p-values of less than 0.05 to be statistically significant.

2.5 Safety and ethical considerations

Isokinetic training is a non-invasive rehabilitation method. A large number of clinical case studies have shown that it can improve muscle strength without serious adverse reactions, indicating that its clinical application is safe. Before carrying out this project, this robot has undergone multiple tests and validations, and its safety can be guaranteed due to its non-invasive nature and the application of flexible joints.

Possible risks during rehabilitation training with isokinetic robots include:

- (1) Improper wearing of the isokinetic training device may cause discomfort in the participant's limbs.
- (2) Overtraining may lead to adverse effects, including muscle soreness, joint pain,

muscle strain or sprain, and fatigue.

(3) Inappropriate posture or failure to follow medical instructions may negatively affect the rehabilitation outcome.

(4) Participants with conditions such as hypertension, hyperlipidemia, obesity, heart disease, diabetes, organ dysfunction, or venous thrombosis may be at increased risk during training.

2.5.1 Definition of Adverse Events (AE) and Serious Adverse Events (SAE)

The definition of adverse events in this experiment is: During the training period and follow-up at the end of the experiment, if the subject experiences knee joint pain without reason, or if there is daily pain but the pain worsens without reason, and there is no improvement after two weeks of the above situation, it is considered an adverse event. If given a certain amount of rest time for recovery and without affecting the observation of therapeutic effects, the experiment can continue. Serious adverse events are those that require hospitalization, extend hospitalization time, disable, affect working ability, cause permanent damage to organ function, endanger life or death, etc. during the clinical experiment. The evaluation of adverse events is divided into five levels: definitely related to training, likely related, possibly related, possibly unrelated, and definitely unrelated. The first three are counted as the incidence of adverse reactions. In case of any serious adverse event or important adverse event, no matter whether it is related to the research intervention or whether the intervention operation has been implemented, it must be reported to the clinical experiment institution and the ethics committee within 24 hours after the occurrence.

Qualification criteria for clinical experiment results:

(1) The relevant data of each subject shall be recorded in the case record form designed according to the requirements of the experiment, and the accuracy and integrity of the data shall be guaranteed, with traceability

(2) Key milestones such as the date of signing the informed consent form, the date of enrollment, and the time of each visit should pay attention to data collection to avoid missing information as much as possible.

(3) The efficacy data recorded during each visit period should be obtained by the subjects strictly following the time window specified in the protocol.

For some subjects who violate the above contents, the main researchers and statistical professionals should discuss and decide the specific treatment measures, and evaluate whether they will have a greater impact on the experiment.

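### The only definition of a non-serious adverse event excludes harms that the protocol itself anticipates, so the adverse-reaction count can only equal or fall below what a wider definition would give

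*Combined protocol and SAP*

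**What the plan says.** Section 2.5.1 opens its definition with "The definition of adverse events in this experiment is: During the training period and follow-up at the end of the experiment". The qualifying event follows: "if the subject experiences knee joint pain without reason, or if there is daily pain but the pain worsens without reason". A duration condition completes it: "there is no improvement after two weeks of the above situation, it is considered an adverse event". Serious adverse events have a separate definition based on their consequences, which is not confined to the knee or to pain.

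Events are then graded for relatedness: "The evaluation of adverse events is divided into five levels: definitely related to training, likely related, possibly related", followed by two levels on the unrelated side. Of these, "The first three are counted as the incidence of adverse reactions". The same section has a continuation sentence, "If given a certain amount of rest time for recovery and without affecting the observation of therapeutic effects, the experiment can continue". It also has a 24-hour reporting rule that begins "In case of any serious adverse event or important adverse event, no matter whether it is related to the research intervention". The term *important adverse event* is not defined.

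Section 2.5 lists the risks that the sponsor expects. A badly worn device may cause limb discomfort. "Overtraining may lead to adverse effects, including muscle soreness, joint pain", and the list goes on to strain or sprain and to fatigue.

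**The concern.** Section 2.5 calls the overtraining harms adverse effects, yet the definition in Section 2.5.1 has no place for several of them. An event that falls outside the definition is not an adverse event under the plan, so it is neither graded nor counted. If the protocol is followed exactly, a child could have training-related fatigue or a thigh strain and contribute nothing to the adverse-reaction incidence.

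The participants are children aged 6 to 12 with SMA type II, using a new wearable device in a study lasting 5.5 months. A low or zero incidence could be read as showing that these harms did not occur, when the rule did not allow them to be counted.

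The same term also governs other provisions. Section 2.3.1 uses it for recording in the case report form and for following up participants who stop because of adverse events. The continuation sentence in Section 2.5.1 depends on it as well.

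**Working it through.** The plan gives no adverse-event figure to reproduce. Its one calculated figure, the sample size in Section 2.3.5, does not depend on this definition. The check is a comparison of texts, followed by a bound on the count.

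**Step 1: the conditions (Section 2.5.1).** A non-serious event must meet all three:
- (a) type: knee joint pain, or worsening of daily pain already present (read generously, at any site);
- (b) cause: *without reason*;
- (c) duration: unimproved at two weeks.

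No other section widens this. Section 2.3.1 uses the term without redefining it. Section 2.3.4 lists knee pain level as a safety outcome but does not link it to the count.

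**Step 2: the anticipated harms (Section 2.5) against the conditions, for non-serious events.**

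| Harm | Meets (a)? | Result |
|---|---|---|
| Fatigue | No; it is not pain | Never counted |
| Soreness, strain or discomfort away from the knee | Only as worsening of daily pain | Not counted when new in a child without daily pain |
| Sprain or device discomfort at the knee | Yes, if it presents as knee joint pain | Counted if (b) and (c) hold and it is graded related |
| Knee joint pain | Yes | Not counted if it improves within two weeks |

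**Step 3: the direction.** Let W be all non-serious untoward events that would be graded in the first three levels if every such event were eligible. Let C be those that also meet (a), (b) and (c). With the same grading, C is a subset of W, so:
- number of events in C ≤ number of events in W;
- number of children with an event in C ≤ number of children with an event in W.

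The two event counts are equal if no excluded event that would be graded related occurs. On a per-child unit, they are also equal if such events occur only in children who already have a counted event. Dividing by a fixed denominator, such as the 6 children, preserves the direction.

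**Step 4: the scale.** Section 2.5.1 states no unit. If the unit is children (an assumption), each child whose only related harms are excluded lowers the incidence by 1/6 = 16.7 percentage points. How many such children there would be cannot be derived, because the documents give neither harm rates nor the number of children with daily pain.

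**Step 5: what else uses the term.** The suspension rule for equipment defects in Section 2.7.1 and the adverse-event termination rule in Section 2.7.3 refer to serious events, so the narrow definition does not reach them. The follow-up provision in Section 2.3.1 and the continuation sentence do use the plain term. On the stated definition, it is unclear whether they cover a child who stops for fatigue or a non-knee strain.

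**The case against.** **Serious harms are caught.** This stands. The serious-event list is open-ended, so the serious route may be wide. The point concerns non-serious events only.

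**Knee pain is measured anyway.** Knee pain level is a safety outcome in Section 2.3.4, so some short-lived knee pain will appear there. This narrows the gap for knee pain. It does nothing for fatigue or non-knee harms, and it does not feed the incidence.

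**The incidence has a minor role.** It is not listed as an outcome in Section 2.3.4 and has no analysis in Section 2.4. That limits the weight of the point, but Section 2.5.1 still prescribes the figure and how to count it.

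**The case report form is not shown.** This is also true, and Section 2.7.2 asks for complete recording. A reader might infer that excluded harms were never written down. The documents show only that the counting rule is narrow.

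**The phrase *without reason*.** Taken literally, it screens out pain explained by training before that pain can be graded definitely related. A reader might conclude that the top grade can never be used. If the phrase means no evident outside trigger, the grading works. The text does not settle this, so it calls for clarification and adds no weight to the conclusion.

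**The true incidence.** A reader might infer that the reported figure must fall below the true incidence of training-caused harm. The documents do not support that. Possibly related events are counted, so persistent knee pain that training did not cause can enter the figure.

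**Conclusion.** The point holds for non-serious events. Section 2.5.1 states a closed definition that several harms anticipated in Section 2.5 cannot meet. The non-serious part of the adverse-reaction count is therefore equal to or lower than the count that the same five-level grading would give with all non-serious untoward events eligible. The gap is clearest for fatigue and for non-knee harms.

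The direction follows from the text, assuming that grading does not change with the definition and, for a proportion, that the denominator is fixed. The size is unknown.

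It would be too strong to say that none of the anticipated harms can be counted, since a sprain or device discomfort at the knee may qualify. It would also be wrong to confine the consequence to the incidence, because the recording, follow-up and continuation provisions share the term. Efficacy outcomes, the two safety outcomes in Section 2.3.4 and the sample size do not depend on it. This should be fixed, but it does not threaten the efficacy analysis.

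**What to change.** **Definition and count.** For recording and counting, define an adverse event as any untoward medical occurrence during the training period and the follow-up that Section 2.5.1 already names, regardless of site, cause or duration. Keep the five-level scale. Compute the adverse-reaction incidence from all such events and state the unit, for example children with at least one event out of 6. Report knee pain unimproved at two weeks separately under its own name, so that *adverse event* has one meaning throughout.

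**Reconciliation.** Bring Sections 2.3.1, 2.5 and 2.5.1 into line. State which events the continuation, follow-up and 24-hour reporting provisions cover; this review proposes no content for those rules. Explain *without reason*. Say what *important adverse event* means and whether such events are graded and counted.

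**If data collection is complete.** The Abstract and Sections 2.3.3 and 2.3.5 are written in the past tense, so this may be the case. Re-review the source records of the six children under the wider definition, and disclose the narrow definition beside any reported incidence.

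**Cost.** The change needs revised wording, possibly a broader case report form entry, and more minor events to log. The reported incidence may rise. In a retrospective review, events never written down may be unrecoverable.

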2.6 Subject protection

According to relevant Chinese laws and regulations, before the start of the experiment, the researcher should make written and oral explanations to the subjects on the background, nature, significance, steps, benefits, risks, withdrawal, etc. of the study, and must obtain the informed consent signed by each subject (or the legal representative of the subject). The informed consent form should indicate the date, and the informed consent form and its copies should be kept separately by the researcher and the subjects.

2.7 Research management system

Before the start of the experiment, the experiment equipment needs to be repeatedly tested to confirm its reliability. The researchers are trained in the Sports Medicine Department of Peking University Third Hospital to be familiar with the experiment process, practical equipment, and assign specific tasks, including subject recruitment, patient guidance, communication, equipment maintenance, data recording, data entry and data processing.

2.7.1 Scheme modification

If there is no significant difference in the experiment results after the plan sample is included. Based on the existing data in this experiment, the sample size will be estimated. The experiment scheme shall be strictly followed. In case of serious adverse reactions caused by equipment defects, the experiment shall be suspended immediately, the defects shall be evaluated, and the decision as to whether the study can be continued will be subject to further ethical approval.

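### Section 2.7.1 requires a pause only when a defect causes a serious reaction; a serious training-related event on a sound device requires no pause for the other children

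*Combined protocol and SAP*

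**What the plan says.** Section 2.7.1 (Scheme modification) holds the only mandatory suspension: "In case of serious adverse reactions caused by equipment defects, the experiment shall be suspended immediately". It goes on: "the defects shall be evaluated, and the decision as to whether the study can be continued will be subject to further ethical approval". Section 2.7.3 (Early termination) adds a mandatory end to the trial after a single serious adverse event related to product quality. Its other grounds are a serious deviation in conduct that makes the training effect hard to evaluate, and a request from the applicant or the administrative department.

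Section 2.5 lists the risks of training on the device. One of them is overtraining: "Overtraining may lead to adverse effects, including muscle soreness, joint pain", followed by strain or sprain and fatigue.

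Section 2.5.1 defines a serious adverse event by its consequences, such as hospitalisation, disability or danger to life. It requires a report to the institution and the ethics committee within 24 hours, whatever the cause. It grades each event on five levels of relation to training and says of these: "The first three are counted as the incidence of adverse reactions". It also lets the study go on after an adverse event if rest is given and observation of the effect is not disturbed.

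Under section 2.3.1 the investigator may withdraw a subject. A child who stops because of an adverse event is followed until it resolves or stabilises.

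**The concern.** The rule for pausing and the stated hazards use different tests. The pause asks whether the device was defective. The risk list and the grading scale ask whether the training did harm. A child could be seriously hurt by too much training on equipment that works as intended, and the mandatory rules would not apply.

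At stake is what happens to the other participants, who are children aged 6 to 12 with type II SMA, while the cause is worked out. Section 2.2 fixes the angular velocity and range of motion for the study, so a problem with the training load may not be confined to one child. As written, whether the others keep training depends on someone choosing to step in. The matter is one of participant safety and does not touch any analysis.

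**Working it through.** No calculated figure in the plan bears on this point. The check is to take one case, a serious event that is related to training and occurs on a sound device, through every provision that could stop or change training.

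| Provision | What sets it off | Acts on | Compels a pause for other children in this case? |
|---|---|---|---|
| 2.7.1 suspension | Serious reaction caused by an equipment defect | Trial | No, there is no defect |
| 2.7.3 termination, first ground | One serious event related to product quality | Trial | No, product quality is not at issue |
| 2.7.3 termination, deviation ground | Serious deviation that makes the effect hard to evaluate | Trial | No, the test concerns evaluability, not safety |
| 2.7.3 termination, request ground | Applicant or administrative department asks | Trial | No, discretionary |
| 2.5.1 report | Any serious event | Institution and ethics committee | No, it is a duty to report; the committee may act on it |
| 2.5.1 grading | Adverse events | The event | No, none of the five grades leads to a pause |
| 2.5.1 rest provision | Follows the definition of an ordinary adverse event | Apparently the affected child | No |
| 2.3.1 withdrawal by the investigator | Investigator's judgement | One subject | No, discretionary and child by child |
| 2.3.1 follow-up | A child stops because of an adverse event | That child | No |

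**Counts.** Trial-level rules made mandatory by a safety event: 2 (2.7.1 and the first ground of 2.7.3). Of these, limited to the device: 2. Relatedness grades: 5. Counted as adverse reactions: 3. Tied to a pause: 0.

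**What the plan does require in this case.** A report within 24 hours, a relatedness grade, and, if the child stops because of the event, recording of the time and reason and follow-up.

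**How many children.** Section 2.3.5 gives 6 recruited, so the others number 6 − 1 = 5 at most. The lower bound is 0, because the readable text does not say whether the children trained at the same time and the study flowchart could not be read.

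**How often.** The documents give no rate of serious events, so no frequency is calculated.

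**The case against.** The best defence is that the asymmetry is deliberate. A defect is a hazard shared by everyone who uses the equipment, whereas poor fitting, posture and pre-existing illness belong mainly to one child. Mandatory suspension for the shared hazard, with rapid reporting for the rest, is a defensible design. Section 2.5 also says of isokinetic training that "it can improve muscle strength without serious adverse reactions", which suggests that the case is rare. The first part stands for most of the listed risks but not for overtraining, since the training load may be common to several children. The second bears on frequency only, and the readable text does not tie that experience to children with SMA.

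A reader might infer that all four risks in section 2.5 escape the rule, because none needs a defect. That claims too much. The first is mild: "Improper wearing of the isokinetic training device may cause discomfort". The third is a poorer result, not an injury: "Inappropriate posture or failure to follow medical instructions may negatively affect the rehabilitation outcome". The fourth concerns pre-existing illness and is partly screened out in section 2.3.1, which excludes severe comorbidities, uncontrolled hypertension and NYHA class III or IV heart failure. Overtraining is the risk that carries the point, and even its listed harms are serious only if they meet the criteria in section 2.5.1.

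A reader might also infer that a defect must be proved before training stops, since section 2.3.1 refers to a final judgement of causation after follow-up. That wording governs what is entered in the case report form. Section 2.7.1 places evaluation after suspension and can fairly be read as acting on the apparent cause.

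Finally, an open-ended halt would itself do harm in a short study. That objection is sound and shapes the fix.

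**Conclusion.** The point holds in a limited form. Both mandatory trial-level safety stops depend on the device, so a serious training-related event on sound equipment leads to reporting, grading and individual follow-up but no required pause for other children. The number exposed is between 0 and 5.

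It would be wrong to conclude that the trial could not be stopped in such a case. The ethics committee receives the report, the applicant or the administrative department may ask for termination, and the investigator may withdraw a child. What is missing is a default that does not wait on these choices.

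The conclusion rests on three assumptions: that the rest provision in section 2.5.1 concerns only the affected child, which is how its position suggests it should be read; that no separate operating procedure sets a pause, since those mentioned in section 2.7.2 are not reproduced; and that training is ongoing or may resume. The abstract and sections 2.3.3 and 2.3.5 use the past tense, and section 2.7.1 provides for re-estimating the sample size without saying that more children will be enrolled. If training is finished and the study is not extended, nothing needs to change. No estimate or test is affected in either case.

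**What to change.** Widen the trigger in section 2.7.1. The sentence could read: *If a serious adverse event is graded definitely, likely or possibly related to training under 2.5.1, or is suspected to result from an equipment defect, training of all participants is paused until the investigator has completed a prompt review of the cause, within a stated time limit, and the ethics committee has responded to the 24-hour report.* Keep the present requirement of renewed ethical approval for confirmed defects, and leave section 2.7.3 unchanged.

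The change uses the grading scale and the report that the plan already has. Hospital admissions judged unrelated to training would fall in the two lower grades and would not set off a pause. The word *suspected* removes doubt about whether a defect has to be established first.

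The drafting cost is one sentence in an amendment. The practical cost is a rare interruption of training dose and visit timing in a 5.5-month study of six children, where section 2.5.1 expects visits to keep to their time windows. That is why the review needs a stated limit. The documents give no basis for a particular number of days, so the investigators should agree it with the ethics committee.
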